7.2.3 Safety Follow-up Visit

Upon permanent discontinuation from the study treatment for any reason, the following procedures will be performed 30 (+ 7) days after the last dose of talimogene laherparepvec:

- Physical examination as per standard of care
- Vital signs (eg, systolic/diastolic blood pressure, heart rate, and temperature)
- Determination of ECOG Performance Status **alongside the tumor response assessments until the end of tumor response assessments per study protocol** ([Appendix E](#))
- Local laboratory assessments:
 - hematology panel: hemoglobin, hematocrit, WBC with 5-part differential (3-part differential if 5-part is unable to be performed), RBC, platelets
 - chemistry panel: sodium, potassium, chloride, total protein, albumin, calcium, creatinine, total bilirubin, alkaline phosphatase, AST, ALT
 - serum or urine pregnancy test for female subjects of childbearing potential

- Central laboratory assessments:
 - swabs of cold sores, vesicles, and other lesions suspected to be herpetic in origin (if any) for qPCR testing:
 - subject should return to clinic within 3 days of the occurrence of a reportable lesion suspected to be herpetic in origin such as cold sores or vesicles. The lesion should be evaluated by the investigator and swabbed if HSV infection is suspected. A qPCR analysis will be performed on the swab sample to evaluate whether the talimogene laherparepvec DNA is detectable in the sample.
- Radiographic tumor imaging, clinical tumor assessments, and tumor response assessments, will be performed as documented in [Section 7.2.2](#) until documented clinically relevant disease progression beyond 6 months of treatment, per modified WHO response criteria ([Appendix D](#)), or until the start of a new anticancer therapy. (Only if subject has discontinued study treatment for reason other than disease progression or death and if not performed within 4 weeks [+1 week] of the safety visit.)
- Recording of adverse events
- Recording of serious adverse events. SAEs will be reported to Amgen within 24 hours following the investigator's knowledge of the event.
- Documentation of concomitant medications

7.2.4 Long-term Follow-up/End of Study

All subjects who permanently discontinue talimogene laherparepvec for any reason other than withdrawal of full consent or death will be contacted by telephone, or clinic visit, to assess survival status and, if applicable, commencement of any subsequent anticancer melanoma therapy. **Adverse events deemed by the investigator to be potentially related to talimogene laherparepvec and use of anti-cancer therapies for melanoma will also be recorded.** Follow-up will occur every 12 weeks (\pm 28 days) following the safety follow-up visit until death, subject withdraws full consent, or up to 24 months after the last subject is enrolled **in the study.**

If subject has discontinued talimogene laherparepvec for reason other than disease progression or death, radiographic tumor imaging, clinical tumor assessments, **ECOG Performance Status assessments, reporting of pregnancy or lactation, assessment of swabs of lesions of suspected herpetic origin for presence of talimogene laherparepvec DNA by qPCR test,** and tumor response assessments will be performed as documented in [Section 7.2.2](#) until documented disease progression beyond 6 months of treatment, per modified WHO response criteria ([Appendix D](#)), until the start of a new anticancer therapy, **or end of study, whichever the earliest.**

After the long term follow-up period of this study has ended, subjects who end the study for any reason other than death or withdrawal of full consent will be followed for survival

under an ongoing separate registry protocol (Study 20120139) that is in place for the long-term follow-up of all subjects treated with talimogene laherparepvec in clinical trials. The registry protocol will also monitor for late and long-term adverse events thought to be potentially related to talimogene laherparepvec **and use of anti-cancer therapies for melanoma.**

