All subjects who permanently discontinue talimogene laherparepvec for any reason other than withdrawal of full consent or death will be contacted by telephone or clinic visit to assess survival, **adverse events thought by the investigator to be potentially related to talimogene laherparepvec, and use of anti-cancer therapies for melanoma** every 12 weeks (\pm 28 days) following the safety follow-up visit until death, subject withdraws full consent, or up to 24 months after the last subject is enrolled **in the study**.

If subject has discontinued talimogene laherparepvec for reason other than disease progression or death, radiographic tumor imaging, clinical tumor assessments, **ECOG Performance Status assessment, assessment of swabs of lesions of suspected herpetic origin by qPCR for talimogene laherparepvec DNA**, and tumor response assessments will be performed until documented disease progression beyond 6 months of treatment, per modified WHO response criteria ([Appendix D](#)), or until the start of a new anticancer therapy **or end of study, whichever the earliest**.

After the long term follow-up period of this study has ended, subjects who end the study for any reason other than death or withdrawal of full consent will be followed for survival under an ongoing separate registry protocol (Study 20120139) that is in place for the long-term follow-up of all subjects treated with talimogene laherparepvec in clinical trials. The registry protocol will also monitor for late and long-term adverse events thought to be potentially related to talimogene laherparepvec **and use of anti-cancer therapies for melanoma**.

Reporting Exposure to Talimogene Laherparepvec:

Reporting potential or known unintended exposure to talimogene laherparepvec, suspected related signs or symptoms, and detection of talimogene laherparepvec in a subject's household member, caregiver, or healthcare provider as specified in [Section 9.4](#)

For a full list of study procedures, including the timing of each procedure, please refer to [Section 7](#) and the Schedule of Assessments ([Table 2](#)).

Statistical Considerations:

All analyses will be descriptive with no formal hypothesis testing. The primary objective of the study is to explore the correlation between baseline intratumoral CD8+ cell density and objective response rate (ORR). The sample size was selected based on practical considerations. The adequacy of the sample size is discussed in [Section 10.2](#).

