7. STUDY PROCEDURES

7.1 Schedule of Assessments

The schedule of assessments for the study is summarized in [Table 2](#)

Table 2. Schedule of Assessments

	Screening ^a	Treatment Period ^b									Follow-up Period	
Cycle ¹	≤ 28 days	1	2	3	4	5	6	7	8	Cycle 8 and Beyond ¹	Safety ^c	Survival ^d
Day		1	1	1	1	1	1	1	1	1	30 (+7) Days	Every 12 (±28 days) Weeks
GENERAL & SAFETY ASSESSMENTS												
Informed Consent	X											
Review of Medical/Surgical History	X											
Review of Eligibility Criteria	X											
Concomitant Medications ^e	X	→										
Adverse and Serious Adverse Events ^f	X	→										
Adverse Events Thought to Be Related to Talimogene Laherparepvec¹		X	→									
Physical Exam ^g	X	X					X			Q6C	X	
Vital Signs ^h	X	X	X		X		X		X	Q2C	X	
ECOG Performance Status ^w	X	X					X			Q6C	X	
Survival Assessment												X
Anti-cancer therapy for melanoma^x											X	X
LOCAL LABORATORY ASSESSMENTS												
Urine or Serum Pregnancy Test ^l	X										X	
Hematology ^l	X	X	X	X				X		Q4C	X	
Chemistry ^x	X	X	X	X				X		Q4C	X	
Serum LDH	X											
PT (or INR) and PTT	X											
CENTRAL LABORATORY ASSESSMENTS												
Archived Tumor Tissue for Biomarker Analysis and BRAF ^{V600E/K1}		Within 28 days after enrollment										
Swab of Herpetic Lesion for qPCR ^m		Within 3 days of occurrence of suspected lesion of herpetic origin									X	X
Blood for HSV Serostatus ⁿ		Within 3 days prior to dose at day 1 of week 1, week 6, and week 12										

Footnotes defined on next page.

Table 2. Schedule of Assessments

	Screening ^a	Treatment Period ^b									Follow-up Period	
Cycle ^t	≤ 28 days	1	2	3	4	5	6	7	8	Cycle 8 and Beyond	Safety ^c	Survival ^d
Day		1	1	1	1	1	1	1	1	1	30 (+7) Days	12 (±28 days) Weeks
Blood for Biomarker Analysis ^o		Within 3 days prior to dose at day 1 of week 1, week 6, week 12, week 24										
Tumor Biopsy for Biomarker Analysis ^p		Within 5 days prior to dose at day 1 of week 1, within 7 days prior to dose at week 6 and within 7 days after the documentation of disease progression followed by treatment discontinuation										
TUMOR/RESPONSE ASSESSMENTS												
Clinical Tumor Assessments ^q	X	Day 1 of week 12 and then every 12 weeks until PD or start of new anticancer therapy									X	X
Radiological Tumor Assessments ^r	X	Day 1 of week 12 and then every 12 weeks until PD or start of new anticancer therapy									X	X
Photographs of all Visible Tumor Lesions ^s (Select Sites Only)		X	X		X		X		X	Q2C		
DOSING												

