- ^p Tumor biopsy **from cutaneous, subcutaneous or nodal lesions** for biomarker analysis **should not be collected prior to the subject being enrolled. Tumor biopsy should be collected** (within 5 days prior to **first** talimogene laherparepvec administration) from one lesion at day 1 of week 1 [**Cycle 1**] and, if there are ≥ 2 lesions at baseline and one is left uninjected as described in [Section 6.2.1.1](#), from an uninjected lesion **within 7 days prior to dose** at day 1 of week 6 [**Cycle 3**]. Also **within 7 days after documentation of disease progression followed by treatment discontinuation** from the **available cutaneous, subcutaneous or nodal** lesion responsible for PD **and easily accessible for biopsy with or without ultrasound guidance**. Note: uninjected lesion biopsied at day 1 of week 6 [**Cycle 3**] must be different lesion from the lesion biopsied at day 1 of week 1 [**Cycle 1**].
- ^q Investigator's clinical measurement of cutaneous, subcutaneous, or nodal tumor by caliper at screening, day 1 of week 12 (± 1 week) [**Cycle 6**] and then every 12 weeks (± 1 week), or more frequently if clinically indicated, until clinically relevant disease progression beyond 6 months of treatment (per modified WHO response criteria, [Appendix D](#)) or until the start of a new anticancer therapy. The screening measurement must be done within 28 days prior to enrollment and will be used as baseline. If subject discontinues talimogene laherparepvec for reason other than disease progression or death, clinical tumor measurements are to be performed at safety follow-up visit (if not performed within previous 4 weeks [+ 1 week]) and every 12 weeks (± 1 week) during the long term follow-up period until clinically relevant disease progression beyond 6 months of treatment (per modified WHO response criteria, [Appendix D](#)) or until the start of a new anticancer therapy.

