Note: uninjected lesion biopsied at day 1 of week 6 must be a different lesion from the lesion biopsied at day 1 of week 1
- Radiographic tumor imaging assessments at day 1 of week 12 (± 1 week) and then every 12 (± 1 week) weeks, or more frequently if clinically indicated, until clinically relevant disease progression beyond 6 months of treatment, per modified WHO response criteria [Appendix D](#)), or until the start of a new anticancer treatment
 - radiographic imaging must include CT scan, PET/CT, MRI, or ultrasound (**if applicable**) of the chest, abdomen, and pelvis and all other sites of disease. In addition, CT scan or MRI of the brain will only be performed if symptoms or signs suggestive of CNS metastasis are present. The imaging modality selected

(eg, CT or MRI) should remain constant **throughout the study** for any individual subject.

- Clinical tumor assessments (clinical measurement of cutaneous, subcutaneous, or nodal tumor measurement by caliper) at day 1 of week 12 (\pm 1 week) and then every 12 (\pm 1 week) weeks or more frequently if clinically indicated, until clinically relevant disease progression beyond 6 months of treatment, per modified WHO response criteria ([Appendix D](#)), or until the start of a new anticancer therapy
- Tumor response assessments at day 1 of week 12 (\pm 1 week) and then every 12 (\pm 1 week) weeks or more frequently if clinically indicated, until clinically relevant disease progression beyond 6 months of treatment, per modified WHO response criteria ([Appendix D](#)), or until the start of a new anticancer therapy
- Photographs of **all** visible cutaneous and subcutaneous tumor lesions **at day 1 Cycle 1, day 1 Cycle 2, and day 1 of every second subsequent cycle** until end of **tumor response assessment per protocol, always within 3 days prior to investigational product administration.** (Select Sites Only: see [Section 7.2.6](#))
- Recording of adverse events at each visit
- Recording of serious adverse events at each visit. Serious adverse events will be reported to Amgen within 24 hours following the investigator's knowledge of the event
- Documentation of concomitant medications at each visit
- Reporting pregnancy in a female subject or a female partner of a male subject while the subject is taking talimogene laherparepvec treatment and through 3 months after end of treatment ([Section 9.3](#))

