Disease Progression (PD):	
A > 25% increase in the sum of the products of the perpendicular diameters of all index tumors since baseline, or the unequivocal appearance of a new tumor since the last response assessment time point.
 
There are 2 types of PD defined in this protocol:
 
Non-clinically relevant disease progression (PDn): PD in subjects who do not suffer a decline in performance status and/or in the opinion of the investigator do not require alternative therapy. Subjects showing overall response as PDn will be allowed to continue study treatment.
 
Clinically relevant disease progression (PDr): PD that is associated with a decline in performance status and/or in the opinion of the investigator the subject requires alternative therapy. Subjects with PDr will be allowed to remain on study until 24 weeks of therapy unless, in the opinion of the investigator, other treatment is warranted.

Stable Disease (SD):	Neither sufficient tumor shrinkage of index lesion to qualify for response (PR or CR) nor sufficient tumor increase of index lesion to qualify for PD.
Unable to Evaluate (UE):	Any index lesion present at baseline which was not assessed or was unable to be evaluated leading to an inability to determine the status of that particular tumor for that time point.
Not Done (ND)	Radiographic image or clinical measurement were not performed at this time point to evaluate the index lesions

Table 6. Definition of Nonindex Lesion Tumor Response

Complete Response (CR):	Disappearance of all nonindex lesions.
Incomplete Response/Stable Disease (SD):	Persistence of one or more nonindex tumor(s).
Disease Progression (PD):	Unequivocal progression of one or more nonindex lesions There are 2 types of PD defined in this protocol: Non-clinically relevant disease progression (PDn): PD in subjects who do not suffer a decline in performance status and/or in the opinion of the investigator do not require alternative therapy. Subjects showing PDn as overall response will be allowed to continue study treatment. Clinically relevant disease progression (PDr): PD that is associated with a decline in performance status and/or in the opinion of the investigator the subject requires alternative therapy. Subjects with PDr will be allowed to remain on study until 24 weeks of therapy unless, in the opinion of the investigator, other treatment is warranted.

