Time to treatment failure is calculated from first dosing until one or more of the following: (1) clinically relevant disease progression(PDr); (2) death from any cause; (3) non-clinically relevant disease progression (PDn) associated with a requirement for

alternative therapy as the reason for ending treatment or start of new anti-cancer therapy. Subjects without an event will be censored at their last evaluable tumor assessment.

This TTF definition is a modified definition of progression free survival (PFS). We do not penalize stopping treatment for CR or lack of injectable disease. In addition, the confirmation of PD is not required.

CCI

Treatment Period

Treatment period is defined as the period between the first date of IP administration in the study and 30 days after the last IP administration in the study.

Treatment-emergent Adverse Events

Treatment-emergent adverse events are defined as any adverse event occurring after initiation of the first dose of IP through 30 days after the last administration of IP in the study. Adverse events that occur on the same day as the first dose date of IP will be treated as treatment-emergent events unless indicated otherwise. (For example, if an event occurs on the same date as the first administration of talimogene laherparepvec and the check box indicating prior to the first dose of IP is checked, then the event will not be counted as a treatment-emergent AE).

Exposure-adjusted Subject Incidence

Exposure-adjusted subject incidence is defined as the number of subjects experiencing a specific event divided by their total subject-time at risk (summation of the time from first drug exposure to first event for subjects with at least one event or to death/end of study/30 days after last IP dose, whichever occurs first for subjects without the event).

Exposure-adjusted Event Rate

Exposure-adjusted event rates is defined as the number of occurrences that subjects experience of a specific event divided by their total subject-time at risk (summation over all subjects). Multiple occurrences of the same event for a subject are counted as events. For each subject, the time at risk will be defined as the start date of IP to death/end of study/30 days after last IP dose, whichever occurs first.

On-study Surgery/procedure

On study surgeries or procedures are defined as surgeries or procedures performed during the treatment period.

[figure not shown]
On-study Death

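### Off-treatment tumour assessment ends at any progression beyond 6 months in Protocol 7.2.4 and the synopsis, but only at clinically relevant progression in the Table 2 footnotes, 7.2.2 and 7.2.3; the looser rule can lengthen time to treatment failure

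*Protocol*

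**What the plan says.** Two rules are given for when tumour assessment ends in subjects who left treatment for a reason other than progression or death.

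- **Unqualified progression.** Protocol 7.2.4, second paragraph, continues assessment "until documented disease progression beyond 6 months of treatment", or until new anticancer therapy or end of study. The synopsis paragraph on long-term follow-up says the same: assessments "will be performed until documented disease progression beyond 6 months of treatment".
- **Clinically relevant progression.** Table 2 footnotes q (caliper measurement) and r (imaging) both address this situation and continue assessment "during the long term follow-up period until clinically relevant disease progression beyond 6 months of treatment". Section 7.2.3 reads "until documented clinically relevant disease progression beyond 6 months of treatment". Section 7.2.2, which 7.2.4 gives as the description of how assessments are done, reads "or more frequently if clinically indicated, until clinically relevant disease progression beyond 6 months of treatment".

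The Table 2 cells for clinical and radiological assessment are shorter still: "Day 1 of week 12 and then every 12 weeks until PD or start of new anticancer therapy".

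Appendix D states "There are 2 types of PD defined in this protocol": PDn, without performance-status decline and/or need for other therapy, and PDr, with one or both.

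SAP Section 6 counts as TTF events PDr, death from any cause, and PDn tied to a need for alternative therapy or the start of new anticancer therapy. It then says "Subjects without an event will be censored at their last evaluable tumor assessment".

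**The concern.** TTF is a named secondary endpoint (Protocol 10.1.1.2). The SAP says that stopping treatment for complete response or for lack of injectable disease is not penalised. For those subjects TTF therefore depends on what is observed after treatment ends.

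If assessment ends at PDn, it ends at a finding that is not itself a TTF event but makes one more likely. A later decline that would turn PDn into PDr has no scheduled scan to record it. Table 2 footnote w also ends scheduled ECOG assessment together with tumour assessment, so the performance-status route to PDr loses its scheduled measurement too. Censoring at that point would follow directly from worsening disease, so it is plausibly informative. With approximately 50 sites planned (Protocol 3.2), some may follow 7.2.4 and others the footnotes.

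**Working it through.** No sample size, power or event count is attached to TTF in either document, so there is no figure to reproduce. The check sets the passages side by side and traces the SAP rules through them.

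**Step 1. Does PDn alone, beyond 6 months, end off-treatment assessment?**

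| Place | Applies to | PDn alone ends assessment? |
|---|---|---|
| Synopsis, long-term follow-up | Off treatment | Yes, read literally |
| 7.2.4, paragraph 2 | Off treatment | Yes, read literally |
| Table 2 footnotes q and r | Off treatment, stated explicitly | No |
| 7.2.3 | Safety follow-up visit | No |
| 7.2.2 | Treatment period; reaches follow-up through 7.2.3 and 7.2.4 | No |
| Table 2 cells | Treatment Period columns; follow-up columns hold only an X | Yes as shorthand, but footnotes q and r govern these rows |

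**Step 2. Is the missing qualifier material?** Yes. Appendix D, cited in the same 7.2.4 sentence, divides progression into two types. The biopsy instruction in 7.2.2 spells out progression as either PDn or PDr. Where the protocol means PDr alone (6.2.1.2, 8.3.1) it adds the qualifier.

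**Step 3. What is still collected once tumour assessment stops?** Section 7.2.4 keeps contact every 12 weeks for survival, subsequent melanoma therapy and related adverse events. Tumour measurement and scheduled ECOG are not among these.

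**Step 4. Trace one subject.** The times are assumed for illustration and do not come from the documents. The subject is off treatment for a reason other than progression. PDn is found at week 48, and a PDr shown by performance-status decline would be found at week 60.

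- (a) Assessment ends only at PDr: TTF event at week 60.
- (b) Assessment ends at PDn, then new therapy or death at week 80: an event is still counted, at week 80 at the latest. The delay is 80 − 60 = 20 weeks.
- (c) Assessment ends at PDn, with neither new therapy nor death by the data cutoff: censored at week 48, the progressing scan.

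Branch (b) takes the event on the date of death or of therapy start. The visible SAP text does not say whether an event of PDn followed by new therapy is dated at the scan or at the start of therapy. If it is dated at the scan, the delay through the therapy route disappears.

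**Step 5. Direction and range.** A late event (b) and censoring at the progressing scan (c) both lengthen estimated TTF. For one subject the error runs from nothing (new therapy starts as soon as PDr would have been called) to complete loss of the event (c).

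**The case against.** The strongest reply is that this is a dropped word. Section 7.2.4 sends the reader to 7.2.2, which carries the qualifier, and footnotes q and r state the off-treatment rule in full. A careful site would probably reach the stricter rule. That is fair as to intent, but 7.2.4 states its own stopping point in the same sentence, and that point differs from the section it cites.

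The consequences also have limits, and several stronger readings that a reader might infer are not supported.

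- *Every subject whose scans stop at PDn is censored there.* No. Death and new anticancer therapy remain observable and count as events. The need-for-therapy route to PDr is largely captured through recorded new therapy.
- *7.2.4 stops at progression whenever it occurs.* No. It and the synopsis apply only beyond 6 months of treatment.
- *The Table 2 cells are a further off-treatment rule.* No. They are treatment-period shorthand that conflicts with its own footnotes.
- *Later responses are lost to ORR or DRR.* Weak. The transient growth in Protocol 3.1 is given as the reason to continue dosing for at least 6 months, whereas this rule applies off treatment and after that. Subjects who stopped for complete response are already responders. Protocol 10.2 puts response onset after 12 months at under 5% of responders.
- *The entry condition, stopping for a reason other than progression, also needs changing.* The synopsis, footnotes q and r, 7.2.3 and 7.2.4 agree on it. Altering it would reconcile nothing and would add scans.

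TTF is also descriptive and secondary, and SAP Section 12 anticipates replacing it with PFS. That lowers the stakes, but TTF is the endpoint in the current documents.

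**Conclusion.** The contradiction stands: two places end off-treatment assessment at unqualified progression beyond 6 months, and the footnotes and sections governing the same assessments require clinically relevant progression. Followed literally, 7.2.4 can leave a later PDr undocumented, giving either a late-dated TTF event or censoring at the progressing scan. Both act in the same direction, towards longer TTF.

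The size cannot be calculated from the documents. They do not give the proportion of subjects who stop for a reason other than progression, then show PDn beyond 6 months, and start no new therapy; nor do they give the interval from PDn to PDr. Any percentage or shift in the median would rest on assumed values for these. The effect is probably modest, because only that subgroup is exposed and because death and new therapy are still recorded. The primary endpoint, the correlation of CD8+ density with ORR, is not shown to be affected. No effect on DOR is claimed, since its definition is not visible in the SAP.

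**What to change.** Use one assessment-stopping rule throughout, matched to the SAP TTF event:

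- In Protocol 7.2.4, paragraph 2, and the matching synopsis paragraph, insert *clinically relevant* before *disease progression*. Footnotes q and r, 7.2.2 and 7.2.3 already use this wording.
- In the Table 2 tumour-assessment cells, replace the bare PD with the stopping point in footnotes q and r.
- Leave the entry condition as it is.
- If TTF is replaced by PFS, check the rule again against the new event definition.

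This concerns the assessment schedule only, not treatment. The cost is protocol wording, plus some 12-weekly assessments at sites that would have stopped at PDn. The footnotes already require those assessments.
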